## 5.6. Interim Analyses and Data Monitoring

No formal interim safety analyses are planned but may be performed if requested by the safety monitoring committee as outlined in protocol section 8.2.18.

Interim immunogenicity analyses will be conducted after all enrolled participants have reached at least week 10 (20.8% of follow-up accrual) and may be conducted at additional time points, if requested by the safety monitoring committee. The main goal of planned interim analyses through week 10 is to assess short-term effect of the candidate vaccine A244/B.63521 (300  $\mu$ g each) with ALFQ adjuvant at the 50, 100, and 200  $\mu$ g doses on cellular and humoral immune responses. This interim group analysis will not compromise the integrity of the trial in terms of the maintenance of the study blind, participant retention, or safety or immunogenicity endpoint assessments. All participant IDs will be replaced with alternate IDs by the unblinded study staff and only the minimum necessary summary level of information will be shared with blinded study staff. Results from planned interim immunogenicity analyses will be used to inform the design of a subsequent clinical trial.

In cases where specific immunogenicity analysis replicates end-of-study endpoints, to minimize the risk of type-I error, an alpha-spending function, such as O'Brien-Fleming boundary will be

used to monitor primary and secondary endpoints using an overall, two-sided alpha of 0.05, with the overall goal being to maximize the amount of alpha reserved for the final study analysis.

### 5.6.1. Humoral Immune Response Interim Analysis

The primary analytical question of interest in the interim analysis is whether significant differences in humoral immune response are observed between dosing regimens. Immune response variables will be determined by the WRAIR lab scientists dependent on sample quality and availability but, in general, will be reflective of those detailed in the primary endpoints (see protocol) and in Section 8 of the SAP. The three dosing groups will be assessed across four visits: weeks 0, 2, 6, and 10. Depending on the statistical technique, the null hypothesis will be that the means or medians do not differ by dosing group.

### Analytical Approach for Immunogenicity Response

To assess differences in humoral immunogenicity response across the three dose groups, linear mixed effects models will be used. The immunogenicity response will be the outcome variable; if necessary, the outcome will be appropriately transformed for inferential analyses and transformed back to the original scale for reporting. The model will include time in days since first injection as a continuous variable, dose group, and an interaction effect between time and dose group. An appropriate method of accounting for covariance will be identified—a likely approach will be to have random intercepts and a random slope for time and an unstructured covariance pattern. A statistically significant interaction effect will indicate that there is a significant difference between groups in the trajectory of the response over time. If a significant interaction effect is observed, pairwise comparisons will be made between groups to determine which group differences explain the significant effect. This approach will not include comparisons between groups at any specific time points; this method precludes having to use an alpha-spending function as these analyses will be qualitatively distinct from those employed in the final analyses.

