9.6.3. Immunogenicity Analysis

The primary immunogenicity endpoint is the magnitude of immune response to the endpoint titer of plasma IgG. Immune response over time (durability) will be assessed by the positive incremental area under the curve (AUC) based on a graph with log endpoint titer on the y-axis and visit week on the x-axis. Summary statistics at specific time points of interest will also be provided using the mean and standard deviation (or median and interquartile range (IQR) as appropriate). Primary comparisons may use a 2-sample t-test with an unadjusted alpha of 0.05. When differences are found, pairwise comparisons between vaccination groups will be made using the Holm-Bonferroni method and a 5% significance threshold for the adjusted p-values.

Further exploratory comparisons may be performed and adjusted for multiplicity as appropriate. Secondary immunogenicity endpoints will entail primarily descriptive analyses. In general, continuous outcomes will be assessed using summary statistics such as the mean, median, standard deviation and IQR. Binary responses will be described using frequencies and percentages. Changes from baseline may be assessed within groups using paired t-tests (or Wilcoxon signed rank as appropriate) or McNemar's test for binary outcomes. Changes over

time between groups may be evaluated using longitudinal models with unstructured covariance matrices where possible or covariance strictures selected as appropriate for the observed data.

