## 4.4. Statistical Considerations for the Study Design

### 4.4.1. Sample Size Considerations

The safety, reactogenicity, and tolerability of the vaccine regimens are the primary endpoints for this study. The table below demonstrates effect size with a power of 80%, calculated at a variety of sample sizes.

Table S3 depicts SAE or AESI rates and associated 95% confidence intervals in each potential grouping of interest given 0-5 participants with observed events. If we were to observe zero events within a single active study group ( $n=20$ ), the upper limit of a 2-sided exact 95% CI would be 13.9% and true events above this could be ruled out at the  $\alpha=0.025$  level.

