**Table S4: Exact 95% Clopper-Pearson CI for the SAE Rate in Each Study Group**

Number of Participants with Event	All Active Groups ( $n=60$ )	Any Active Group ( $n=20$ )
0	0% (0%, 4.9%)	0% (0%, 13.9%)
1	1.7% (<0.1%, 8.9%)	5.0% (0.1%, 24.9%)
2	3.3% (0.4%, 11.5%)	10.0% (1.2%, 31.7%)
3	5.0% (1.0%, 13.9%)	15.0% (3.2%, 37.9%)
4	6.7% (1.8%, 16.2%)	20.0% (5.7%, 43.7%)

Number of Participants with Event	All Active Groups (n=60)	Any Active Group (n=20)
5	8.3% (2.8%, 18.4%)	25.0% (8.7%, 49.1%)

Table S4 presents the estimated power for the secondary outcome of antibody titer based on the published data from Pitisuttithum P et.al. For the analysis of this experiment, we plan on observing a single measurement of peak antibody level per participant. Thus, the study is designed around a 1-way ANOVA model. Tukey's method will be used in the pairwise comparison test. In the analysis, we looked at the size of the error bars on the peak of the log antibody titer and based upon our visual inspection we assumed that the residual standard deviation is = 0.2. A sample size of approximately 20 participants per arm was selected to provide  $\geq 80\%$  power to detect the effect size of  $\geq 0.202$  between study arms. Statistical significance will be set at  $p \leq 0.05$ .

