## **5.7. Multiple Comparisons/Multiplicity**

All hypothesis tests will be performed as two-sided at the 5%-level, including planned immunogenicity analysis. Due to the limited sample size and the early phase of the study, adjustment for multiplicity across endpoints will not occur. For individual endpoints that involve a multitude of hypothesis testing (e.g., gene expression), the analysis will be adjusted for multiplicity using the Bonferroni-Holm step-down procedure [3]. Results will be considered on the strength of evidence. P-values  $\leq 0.05$  will be considered statistically significant evidence of a difference or association.

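### The interim humoral test fits one straight line in time; with the covariance the SAP calls likely, shared curvature can cost it anywhere from little to nearly all of its power

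*SAP*

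**What the plan says.** SAP 5.6.1 makes a difference in humoral response between regimens the main question of the interim, assessed at weeks 0, 2, 6 and 10. On the model, the subsection on the analytical approach says: "The model will include time in days since first injection as a continuous variable", together with dose group and their interaction. No quadratic, spline or categorical visit term is named there. The covariance is left to be identified later; the structure named as likely is "random intercepts and a random slope for time" with an unstructured pattern. Pairwise comparisons follow only if the interaction is significant. Comparisons at single visits are ruled out, and the SAP gives this as the reason no alpha-spending is needed.

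The next subsection plans an ANOVA of area under the curve from week 0 to week 10 and allows a cubic spline there if inflections appear. SAP 5.6 says the interim results will inform a later trial.

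Protocol 9.6.3 says that changes over time between groups may be evaluated with "longitudinal models with unstructured covariance matrices where possible". It does not mention visit as a categorical factor.

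**The concern.** Each post-baseline interim visit falls two weeks after one more dose, but the gaps between visits are 14, 28 and 28 days. A straight line over days 0, 14, 42 and 70 needs the first dose to produce 14/70 = 20% of the total rise and each later dose 28/70 = 40%. Even equal increments per dose bend away from that line.

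In a random-intercept and random-slope fit, the part of the common mean that the line misses is treated as residual noise. The random-slope variance tends to collapse to its boundary and the standard error of the dose-by-time effect becomes too large. The test asks the SAP's question with the wrong yardstick. A non-significant interaction could then be misread as no dose difference when the next trial is designed.

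**Working it through.** **Inputs from the documents.** Three arms of 20; two-sided 5% (SAP 5.7: "All hypothesis tests will be performed as two-sided at the 5%-level"); outer-arm difference 0.202; SD 0.2, obtained by "visual inspection we assumed that the residual standard deviation is = 0.2".

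**Assumptions not in the documents.** Log10 scale; baseline SD 0.05; correlation 0.5 between post-dose visits; middle arm at the midpoint; the mean profiles below; nominal days; no dropout.

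**1. The plan's own figure.** It belongs to the peak-titre design ("Thus, the study is designed around a 1-way ANOVA model"), not to this test. λ = n(d²/2)/SD² = 20 × (0.202²/2)/0.04 = 10.2. With 2 and 57 df and critical F 3.16, power is 0.802, as in the plan. No power is stated for the interaction.

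**2. Power of the slope contrast with a valid standard error.** Scale time so that day 70 = 1: t = 0, 0.2, 0.6, 1.0, mean 0.45, Sxx = 0.59. Each participant's slope has weights (t − 0.45)/0.59 = −0.763, −0.424, 0.254, 0.932.

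- Post-dose part of its variance: 0.04 × [0.5 × (0.424² + 0.254² + 0.932²) + 0.5 × (−0.424 + 0.254 + 0.932)²] = 0.04 × (0.5 × 1.113 + 0.5 × 0.582) = 0.0339.
- Baseline part, taken as independent: 0.763² × 0.0025 = 0.0015.
- Total v = 0.0354.

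For a difference growing in proportion to time up to 0.202, λ = 20 × 0.0204/0.0354 = 11.5 and power is 0.85. On complete data this is an ANOVA of participants' own slopes, and equally the slope contrast in a categorical-visit model with unstructured covariance.

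**3. What curvature does.** With slope variance at zero, the standard error of the slope difference between two arms is σ√(2/(n·Sxx)). In one simulated fit with rises 1.0/2.0/2.5, σ was 0.294, giving 0.294 × √(2/11.8) = 0.121. Participants' own slopes gave 0.055, so the ratio r is 2.2.

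If the standard error is inflated by r, F is divided by r², so power is P{F(2, 57; λ) > 3.16r²}:

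| r | effective critical F | power, λ = 11.5 | type I error |
|---|---|---|---|
| 1.0 | 3.16 | 0.85 | 0.05 |
| 1.15 | 4.18 | 0.74 | 0.02 |
| 1.5 | 7.11 | 0.42 | 0.002 |
| 2.5 | 19.7 | 0.01 | <0.001 |

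**4. Simulation of the REML fit** (150 to 300 trials per cell, Monte Carlo error about 0.03 to 0.04), SD 0.2, correlation 0.5, growing difference. Ranges are from separate runs.

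| mean rise at weeks 2/6/10 | r | random-slope model | same contrast, valid SE |
|---|---|---|---|
| exactly linear | 1.1–1.15 | 0.73–0.81 | 0.84–0.88 |
| equal steps, total 1.0 | 1.2 | 0.76 | 0.88 |
| equal steps, total 2.0 | 1.4 | 0.58 | 0.85 |
| 0.5/1.5/2.0 | 1.5–1.6 | 0.46–0.49 | 0.88 |
| equal steps, total 2.5 | 1.5 | 0.45 | 0.88 |
| 1.0/2.0/2.5 | 2.2 | 0.03 | 0.87 |
| 1.0/2.5/3.0 | 2.5–2.7 | 0.00 | 0.88–0.92 |

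For a difference that is constant after dose 1, equal steps totalling 2.5 gave 0.14 against 0.61.

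**5. When the loss shrinks.** With a true spread of slopes, equal steps totalling 2.5 at SD 0.2 gave 0.62 against 0.78. The 1.0/2.0/2.5 profile gave 0.11 against 0.77 at SD 0.2, 0.64 against 0.78 at SD 0.4, and 0.72 against 0.78 at SD 0.6.

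**6. The alternative gate.** The joint dose-by-visit test with unstructured covariance, over equal-step profiles, gave 0.64 to 0.72 for growing differences and 0.74 to 0.80 for constant ones. The slope contrast with a valid standard error gave 0.85 to 0.88 and 0.57 to 0.61 respectively.

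**The case against.** The strongest reply is that the SAP has not committed to the model that fails. Random intercept and slope is only the likely choice, and the unstructured pattern could be read as applying to the residuals as well as to the random effects. That stands. With the same linear mean and an unstructured residual covariance, power for the growing difference was 0.82 to 0.88 at correlation 0.5, with or without curvature. This is a reason to settle the covariance now.

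Four stronger readings are tempting, and the documents do not support them:

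- **That the test loses most of its power.** The documents give no trajectory, within-person correlation or slope spread, and across plausible values the loss runs from little to nearly all.
- **That the mean cannot be linear.** Weeks 4 and 8 are not in the interim model, so a near-linear rise is possible. The small deficit in the exactly linear case comes from the assumed tight baseline, not from curvature.
- **That a real dose difference would usually be reported as none.** The AUC ANOVA addresses the same question. Under the assumptions above, its power on the log scale is about 0.92 for a constant difference, though only about 0.45 for a growing one.
- **That the protocol already prescribes categorical visit.** It names only the covariance.

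Using actual days is also a deliberate choice: the SAP revision history records out-of-window vaccinations.

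**Conclusion.** The concern holds in conditional form. A single linear term, combined with the covariance the SAP calls likely, gives a conservative gate (type I error about 0 to 0.02) whenever the common mean is noticeably curved. At SD 0.2 and correlation 0.5, power for a difference growing to 0.202 is about 0.45 instead of 0.85 for rises 0.5/1.5/2.0, and near 0 instead of 0.85 for 1.0/2.5/3.0. The loss is small for nearly linear rises, and smaller when the SD is larger or participants truly differ in slope.

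The direction does not depend on the choice between slopes and other contrasts: at SD 0.2 and correlation 0.5, the same slope contrast with a valid standard error had more power than the random-slope model in every cell above. The absolute figures rest on the listed assumptions and on an SD read by eye. The change is a worthwhile, inexpensive improvement to an interim test. It does not bear on the primary safety analysis.

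**What to change.** In SAP 5.6.1, replace the linear-time model with visit (weeks 0, 2, 6, 10) as a categorical factor, dose, dose-by-visit and an unstructured residual covariance. Name one gate in advance:

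- **The slope (linear-trend) contrast within that model**, which keeps the SAP's question with a valid standard error. It is weak for differences confined to early visits (0.12 to 0.16, against 0.76 to 0.79 with the joint test).
- **The joint dose-by-visit test**, which is stronger for early or constant differences but not for growing ones.

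Neither is a comparison at a single visit, so that SAP restriction is kept. Add a sentence that a non-significant interaction is not evidence of equal response and is to be read with the AUC result.

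The cost is SAP wording, on the same data and with standard software. The downside is that nominal visits replace actual days. Out-of-window samples would follow the rule already in SAP 5.5, which assigns them to the intended visit and examines their exclusion in sensitivity analyses.

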### Area under the Response Curve

Mean area under the curve (AUC) can be used to represent the time and population averaged immune response from week 0 to week 10. Time will be measured in days since first injection and reflect the date of sample collection (rather than visit number). Immunogen response distribution will be assessed for each visit for overall homogeneity of response pattern independently for each group. Time-normalized values will be calculated for AUC (denoted as nAUC) to account for differences in follow-up time due to early drop-out or missing data. Individual nAUC may be calculated via the trapezoidal method as:

$$\frac{1}{T} \sum_{i=1}^m \frac{Y_{i,j}}{T} + \frac{\tilde{T}}{2} \frac{1}{T}$$

Where  $\frac{1}{T} \sum_{i=1}^m \frac{Y_{i,j}}{T}$  is the normalized AUC for an individual;  $T$ =total observation time for individual  $i$ ;  $Y_{i,j}$ =humoral response of individual  $i$  at time  $j$ ,  $m$ =number of timepoints for individual  $i$ ,  $t_{i,j}$ =time in days for individual  $i$  at time  $j$ .

If the data reflects apparent inflection points, a cubic spline function may be used to estimate the functional form of the response data, and the nAUC may be derived using the definite integral of

the response curve from v0 to v10 to account for the data's inflection tendencies. Estimation of nAUC may also be derived through applications of a linear mixed effect model following methods outlined in Alexandre (2021) for group level effects, with or without the inclusion of additional covariates.

ANOVA will be used to assess differences in AUC between groups. Normality assumptions for immunogenicity marker AUC will be assessed. If strong departures from normality are observed data will be transformed to achieve normality; log transformations will be prioritized but other transformations will be explored as appropriate for optimal fit. In the case where normality transformations perform poorly, a Kruskal-Wallis analysis will be used incorporating appropriate adjustments for equivalence testing.

### **5.6.2. Cellular Immune Response Interim Analysis**

Cellular immune responses mediated by T lymphocytes will also be assessed in the interim analysis. Cellular immune response variables will be determined by the WRAIR lab scientists dependent on sample quality and availability but, in general, will be reflective of those detailed in the primary endpoints (see protocol) and in Section 8 of the SAP. The three dosing groups will be assessed across four visits: weeks 0, 2, 6, and 10. Depending on the statistical technique, the null hypothesis will be that the means or medians do not differ by dosing group.

#### **Analytical Approach for Cellular Immunogenicity Response**

The overall magnitude and quality of the antigen-specific T cell response will be assessed through detection of cytokine expression measured by flow cytometry. Measures at pre-vaccination and 2 weeks after each vaccination (weeks 2, 6, 10) will be assessed from all individuals divided by vaccination group. Levels of antigen-specific T cells will be compared between groups at both timepoints for Total responses (Boolean gating of flow cytometry data will be used to assess) and individual cytokines (IL-21, IL-2, TNF-a, IL-4, IFN- $\gamma$ , CD154). Polyfunctional scores and Heatmap of posterior probabilities via COMPASS analysis will be assessed using R software.

## **5.7. Multiple Comparisons/Multiplicity**

All hypothesis tests will be performed as two-sided at the 5%-level, including planned immunogenicity analysis. Due to the limited sample size and the early phase of the study, adjustment for multiplicity across endpoints will not occur. For individual endpoints that involve a multitude of hypothesis testing (e.g., gene expression), the analysis will be adjusted for multiplicity using the Bonferroni-Holm step-down procedure [3]. Results will be considered on the strength of evidence. P-values  $\leq 0.05$  will be considered statistically significant evidence of a difference or association.

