9.6.6. Planned Interim Analyses

No formal interim safety analyses are planned but may be performed if requested by the safety monitoring committee as outlined in Section 8.2.18.

Interim immunogenicity analyses will be conducted after all enrolled participants have reached at least week 10 (20.8% of follow-up accrual) and may be conducted at additional time points if requested by the safety monitoring committee. The main goal of planned interim analyses through week 10 is to assess short-term effect of the candidate vaccine A244/B.63521 (300 µg each) with ALFQ adjuvant at the 200, 100, and 50 µg doses on cellular and humoral immune responses. This immunogenicity group analysis will not compromise the integrity of the trial in terms of the maintenance of the study blind, participant retention, or safety or immunogenicity endpoint assessments. All participant IDs will be replaced with alternate IDs by the unblinded study staff and only the minimum necessary summary level of information will be shared with blinded study staff. Results from planned interim immunogenicity analyses will be used to inform the design of a subsequent clinical trial.

To minimize the risk of type-I error, an alpha-spending function, such as O'Brien-Fleming boundary will be used to monitor primary and secondary endpoints using an overall, two-sided alpha of 0.05, with the overall goal being to maximize the amount of alpha reserved for the final study analysis. Specific details of alpha-spending methods will be included in the statistical analysis plan.

The Principal Investigator will ensure concurrence from USAMRDC ORA as outlined in Section **Error! Reference source not found.** prior to presentation or publication of data from interim analyses. Any analyses conducted prior to the end of the scheduled follow-up visits will not compromise the integrity of the trial in terms of participant retention or safety or immunogenicity endpoint assessments.

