Total immune responses over time will be assessed by the positive incremental area under the curve (AUC). An AUC curve will be constructed with raw, unlogged endpoint titers on the y-axis and visit week on the x-axis (week 0 to week 48). AUC will be logged after calculation from raw values. For comparability between participants with different numbers of samples (visits) available, these values will be scaled (normalized) by the week of the last available sample. If no sample is available for visits other than the first and last, no explicit imputation will be done, and the AUC will be calculated based on available samples. Log AUC will be analysed similarly to the visit-by-visit titers and presented as mean AUC and 95% CI.

The magnitude of CD4+ and CD8+ T-cell effector function and polyfunctionality will be evaluated through response by cytokines such as IFN- $\gamma$  and IL2. The frequencies of CD4 or CD8 T cells responding to each test antigen with IFN- $\gamma$  and/or IL2 will be calculated using the following categories: all IFNy+, all IL2+, IFNy and IL2+, IFNy or IL2+. Descriptive statistics will evaluate the distribution of CD4+ and CD8+ responses and polyfunctionality scores by vaccination group and visit. Differences in CD4+ and CD8+ responses between vaccination groups at each visit will be evaluated using Kruskal-Wallis tests, and pair-wise comparisons of

particular visits will be performed with two-sided Mann-Whitney U test, with a Bonferroni-Holm step-down for adjusting p-values for multiple comparisons.

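### SAP 5.6 and 5.7 give different significance thresholds for the interim T-cell comparisons by visit, although the data for those visits are complete at the interim

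*SAP*

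**What the plan says.** Three passages set the interim threshold.

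- SAP 5.6: "In cases where specific immunogenicity analysis replicates end-of-study endpoints, to minimize the risk of type-I error, an alpha-spending function, such as O'Brien-Fleming boundary" is to be used, within an overall two-sided 0.05.
- Protocol 9.6.6 has the same spending rule without the condition that an endpoint be repeated, and leaves the details to the SAP. The SAP supplies no boundary, no information fraction and no list of repeated endpoints.
- SAP 5.7: "All hypothesis tests will be performed as two-sided at the 5%-level, including planned immunogenicity analysis". Any p-value at or below 0.05 "will be considered statistically significant evidence of a difference or association".

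SAP 5.6.1 exempts the humoral mixed model, on the ground that it makes no group comparison at a particular time point: "this method precludes having to use an alpha-spending function as these analyses will be qualitatively distinct from those employed in the final analyses".

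For the cellular interim, SAP 5.6.2 says: "Measures at pre-vaccination and 2 weeks after each vaccination (weeks 2, 6, 10) will be assessed from all individuals divided by vaccination group". It then compares T-cell levels between the groups, both as total responses and for single cytokines that include IFN-γ and IL-2. In the final analysis (SAP 8.1), "Differences in CD4+ and CD8+ responses between vaccination groups at each visit will be evaluated using Kruskal-Wallis tests".

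The interim is timed "after all enrolled participants have reached at least week 10 (20.8% of follow-up accrual". SAP 5.6 repeats this figure.

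**The concern.** A T-cell comparison at week 2, 6 or 10 that appears in both the interim and the final analysis falls under two rules. SAP 5.6 calls for a spending boundary. SAP 5.7 calls for 0.05. Nothing says which prevails, and the reason given for exempting the humoral mixed model does not apply, because the cellular interim does compare groups at particular visits.

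The interim results are to feed into the design of the next trial. As written, the threshold for calling an arm difference significant would be chosen when results by group are already in view. An interim T-cell p-value of 0.001 is significant under 5.7. Under 5.6 it might not be, depending on a boundary and a fraction that the SAP never states.

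**Working it through.** **1. Where 20.8% comes from.** 10/48 weeks = 0.2083, and 70/336 days gives the same. Counting to the last telephone contact, 10/56 = 0.179, does not fit. The figure is therefore the share of calendar follow-up to the last clinic visit.

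**2. Information actually available.** Every enrolled participant has reached week 10 when the interim starts.

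| Endpoint (SAP 8.1) | Last visit needed | Complete at interim? |
|---|---|---|
| Comparison at week 2, 6 or 10 | that visit | yes, fraction 1 |
| Peak titer across all visits | week 48 | no |
| Durability | weeks 24 and 48 | no |
| AUC, weeks 0 to 48 | week 48 | no |

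**3. Threshold under spending.** The O'Brien-Fleming-type function at information fraction t is

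α(t) = 2[1 − Φ(z₀.₉₇₅/√t)].

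- t = 10/48: 1.96/√0.2083 = 4.294, so α = 1.75e-5. This is 0.05/1.75e-5, or about 2,850 times below 5%.
- t = 10/48, spending 0.025 on each side: 4[1 − Φ(z₀.₉₈₇₅/√t)] = 1.8e-6.
- t = 1: α = 0.05. With the fraction that is right for these visits, spending releases the whole 5% and the two rules agree.

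**4. Type I error if 5% is used at both looks.** This is the chance of at least one rejection under the null, bivariate normal, with correlation ρ between the interim and final statistics.

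| ρ | Situation | Type I error |
|---|---|---|
| √(10/48) = 0.456 | endpoint truly at 20.8% information | 9.2% |
| 0.7 to 0.95 | assumed range, not in the documents | 8.3% to 6.5% |
| about 1 | same test, same complete data | about 5% |

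Spending has a purpose in the first two rows. It has none in the third, which is where the comparisons at weeks 2, 6 and 10 lie.

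**5. Power, as illustration only.** Inputs are those of protocol 9.4 and SAP 4.4.1 for the peak antibody titer: three arms, n = 20 each, SD 0.2, largest difference 0.202, one-way ANOVA. With means at −0.101, 0 and +0.101, the noncentrality is λ = 20 × (2 × 0.101²)/0.2² = 10.2, with 2 and 57 degrees of freedom.

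| Two-sided α | Power at 0.202 | Difference detectable with 80% power |
|---|---|---|
| 0.05 | 0.8017 (plan: 0.802) | 0.202 |
| 1.75e-5 | 5.0% | 0.379 |
| 1.8e-6 | 1.5% | 0.421 |

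The first row reproduces the plan's own figure.

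**The case against.** The strongest reply is that the size of the conflict is inferred. The documents use 20.8% to describe timing and nowhere assign it to the boundary, and O'Brien-Fleming is named only as an example. With t = 1 the two rules give the same threshold. This stands. A reader might infer that the plan tests week-10 endpoints at about 1.8e-5, but the documents do not say so. What remains is that 5.6 and 5.7 conflict as worded, and that the only fraction printed beside the spending rule is wrong for these visits.

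Three other stronger readings also fail.

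- That the T-cell tests lose power from 80% to 5%. The inputs belong to the peak antibody titer. The documents give no T-cell variance, and the final T-cell test is Kruskal-Wallis.
- That the SAP rules out spending for all interim tests. The exemption in 5.6.1 is limited to the humoral mixed model, so there is no general statement to delete.
- That the interim and final T-cell analyses are identical. The interim uses total responses and six markers, names no test, speaks of two time points without naming them, and leaves the choice of variables to the laboratory. The final analysis uses IFN-γ and IL-2 categories. The overlap shown is partial.

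It is also fair that the trial describes itself as exploratory, that immunogenicity is secondary and mainly descriptive, and that no stopping rule hangs on an interim p-value. This limits the consequence. It does not settle which threshold applies. Nor can 5.7 be read as only an overall 5% level, since it also declares each p ≤ 0.05 significant.

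**Conclusion.** The point holds as a contradiction between SAP 5.7 on one side and SAP 5.6 and protocol 9.6.6 on the other. It clearly affects the T-cell comparisons by visit through week 10, at least for IFN-γ and IL-2. For those visits spending protects nothing, because repeating an unchanged test on complete data leaves the error at about 5%. This assumes that the assay data for those visits are final at the interim and are not re-run or added to later.

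The threshold could differ by a factor of about 2,850 or more, and power could fall from 80% to about 5% or 1.5%, but only if an analyst took 20.8% as the spending fraction. The power figures are borrowed from the antibody design. The contradiction itself depends on neither. It is worth correcting, because the interim informs the next trial and the correction is small.

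**What to change.** In SAP 5.6 and 5.7:

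- State that comparisons by visit, for visits complete at the interim (through week 10), have full information. Test them once at two-sided 5%, with Holm for the pairwise comparisons, and carry the results forward unchanged as the final analysis of those visits. Apply no alpha spending to them and make no use of the 20.8% figure.
- List which interim tests repeat a final endpoint, and name the T-cell variables, visits and test.
- Test endpoints that need weeks 24 or 48 (AUC to week 48, durability, peak across all visits) at end of study. If any of them is also tested at the interim, state the spending function and an information fraction specific to that endpoint, and add this exception to 5.7.
- Keep the exemption in 5.6.1 and say that it covers the humoral mixed model only.

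Align protocol 9.6.6, whose spending rule has no repetition condition, or record the change as a deviation from the statistical plan under protocol 9.2. Changing the SAP alone would leave the two documents in conflict.

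The cost is SAP wording plus that alignment. No extra data, visits or participants are needed.
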